16.1.2 Descriptive Statistics of PK Parameter Data

PK parameter data of evobrutinib on Day 1 will be descriptively summarized by study intervention and day using Mean, SD, CV%, Min, Median, Max, geometric mean (GeoMean), the geometric coefficient of variation (GeoCV%) and the 95% confidence interval (CI) for the GeoMean (LCI 95% GM, UCI 95% GM). For PK parameters related to time (e.g. t_{max} , t_{lag} , t_{last}), only n, Min, Median, and Max may be reported.

Descriptive statistics will only be calculated for a PK parameter when $n > 2$.

PK parameters read directly from the measurements (i.e., C_{max}) will be reported with the same precision as the source data. All other PK parameters will be reported to 3 significant figures. In export datasets, as well as in the SDTM PP domain, PK parameters will be provided with full precision and will not be rounded. Descriptive statistics of PK parameter data will be calculated using full precision values and rounded for reporting purposes only.

The following conventions will be applied when reporting descriptive statistics of PK parameter data:

n	0 decimal place
Mean, Min, Median, Max, GeoMean, 95% CI:	3 significant digits
SD:	4 significant digits
CV%, GeoCV%:	1 decimal place

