## Evobrutinib (M2951) Relative Bioavailability of Evobrutinib Tablet Batches

MS200527\_0131

Assessment	Screening	Treatment								SFU by phone	Comments	
		P1		P2		P3		P4				
Study Day(s)	-28 to -2	-1	1	2	3	4	5	6	7	8	15 ± 3	Approximate 48-hour washout between doses on Days 1, 3, 5, and 7.
Period-specific Day(s)	-28 to -2	-1	1	2	1	2	1	2	1	2		
Administration of study intervention			X		X		X		X			Washout period of 48 hours.
Physical examination	X	X							X			A full physical examination will be performed at Screening and before discharge on Day 8, and a brief physical examination will be performed on Day -1.
Vital signs	X	X	X		X		X		X	X		Vital signs will be assessed on the days of dosing (Day 1, 3, 5, and 7) at predose and at 2 hours postdose. At visits where assessment time points coincide with each other, the following sequence of activities will be followed: 12-lead ECG followed by vital signs within 30 minutes before the specified time point preceding the PK sampling, which will be performed at the specified time point.
Safety ECG	X	X	X		X		X		X	X		12-lead ECG will be performed on the days of dosing (Day 1, 3, 5, and 7) at predose and at 2 hours postdose. See Vital signs (row above) for assessments that coincide.
Clinical laboratory safety tests	X	X					X		X			On Day 5, tests will be performed predose. Blood samples for the clinical laboratory safety assessments will be collected in a fasted condition.
PK sampling			X	X	X	X	X	X	X	X		Plasma samples for PK analysis will be collected on the days of dosing (i.e., Days 1, 3, 5, and 7) at predose and 0.25, 0.5, 1.0, 1.5, 2.0, 2.5, 3.0, 4.0, 6.0, 8.0, 12.0, 16.0, and 24.0 hours postdose. See Vital signs (row above) for assessments that coincide.
Previous medication	X											
Concomitant medication monitoring	X	<=====>						X				
AE monitoring	X	<=====>						X				

AE=Adverse Event, Day = Study Day, ECG = Electrocardiogram, eGFR = estimated Glomerular Filtration Rate;FSH = Follicle stimulating hormone, P=Period, PK=Pharmacokinetics.

CONFIDENTIAL  
INFORMATION

10/60

Global Version ID: CCI

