### 2.1                **Study Rationale**

The purpose of this study is to compare evobrutinib PK profiles for 45-mg IR tablet (TF2 formulation) batches that have shown varying dissolution profiles in vitro. The relative bioavailability of the batches will be assessed in reference to a reference batch. The choice of the reference and test batches is based on in vitro dissolution profiles: 1 each of lower and upper dissolution bounds (termed side batches), 1 batch as a reference (all 3 batches being conical sieve milled), and a 4th batch which is hammer-milled. This approach, referred to as mapping methodology, is described in the FDA guidance on dissolution testing for immediate release solid oral dosage forms (Guidance for industry, Dissolution testing of immediate release solid oral dosage forms, 1997). Primary PK parameters assessed include evobrutinib plasma  $C_{max}$  and  $AUC_{0-\infty}$ .

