## 4.2            Scientific Rationale for Study Design

This study will compare the single-dose evobrutinib PK of different tablet manufacturing batches relative to a reference batch under fasted conditions in healthy participants. Results of this study are planned to provide data to support ongoing clinical development and post-approval activities.

The study utilizes a randomized crossover design to ensure all participants who complete the study receive each treatment and hence allows within participant comparisons, and that no bias is introduced or confounds the conclusions of the study. [CCI](#)

[REDACTED]

[REDACTED]

The study endpoints are based on the regulatory guidance of the FDA (Bioavailability and Bioequivalence Studies Submitted in NDAs or INDs — General Considerations, 2014) and the EMA (Guideline on the Investigation of Bioequivalence, 2010).

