#### 9.4.3                    Other Analyses

Category/Endpoint	Statistical Analysis Methods
Primary	
AUC 0-∞ C max	PK parameters are listed in Section 8.4. Summary statistics will be provided. A linear mixed model with BATCH, PERIOD, and SEQUENCE as fixed effects and SUBJECT within SEQUENCE as a random effect will be applied to log-transformed primary endpoints C max , and AUC 0-∞ based on the PK analysis set. Differences between batches on the log scale for each comparison will be estimated for the parameters together with their 90% CIs. Point estimates and CIs will be back transformed to the original scale for presentation.  All PK analyses will be performed on the PKAS.
Secondary	
PK parameters (in Section 8.4)	Summary statistics of PK parameters will be provided. All PK analyses will be performed on the PKAS.

PKAS = PK analysis set.

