16.1.3 Statistical Analysis of PK Parameter Data

Analysis of Primary Endpoints

A linear mixed model with BATCH, PERIOD, and SEQUENCE as fixed effects and SUBJECT within SEQUENCE as a random effect will be applied to log-transformed primary endpoints C_{max} and $AUC_{0-\infty}$ based on the PK analysis set. Differences between batches (treatment A will be used as 'reference') on the log scale for each comparison will be estimated for the parameters together with their 90% CIs. Point estimates and CIs will be back transformed to the original scale by exponentiation for presentation. Ratio of geometric LSMEAN with 90% CI and geometric LSMEAN with 95 % CI will be presented.

Analysis of Secondary Endpoints

Summary statistics of PK parameters will be provided by study intervention.

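### tmax, a secondary endpoint, is summarised only batch by batch, with no within-participant difference from the reference batch and no interval

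*SAP*

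**What the plan says.** Protocol 2.1 explains that the study compares "batches that have shown varying dissolution profiles in vitro". Protocol 4.2 justifies the crossover because all completers "receive each treatment and hence allows within participant comparisons". Protocol 3 and SAP 5 list tmax among the secondary PK endpoints.

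The analysis text splits the endpoints in two:

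- **Primary (Cmax and AUC0-∞).** SAP 16.1.3 applies "A linear mixed model with BATCH, PERIOD, and SEQUENCE as fixed effects and SUBJECT within SEQUENCE as a random effect", and batch differences "will be estimated for the parameters together with their 90% CIs", with Batch A as reference.
- **Secondary, including tmax.** SAP 16.1.3 says "Summary statistics of PK parameters will be provided by study intervention". Protocol 9.4.3 says "Summary statistics of PK parameters will be provided. All PK analyses will be performed on the PKAS". For parameters measured in time, SAP 16.1.2 adds that "only n, Min, Median, and Max may be reported".

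Plasma is sampled at "predose and 0.25, 0.5, 1.0, 1.5, 2.0, 2.5, 3.0, 4.0, 6.0, 8.0, 12.0, 16.0, and 24.0 hours postdose" (Protocol 1.3). SAP 16.1.5.1 takes tmax directly from the observed profile and uses actual elapsed time. SAP 16.1.6 lists individual parameters by participant and batch, and overlays each participant's profiles.

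**The concern.** A change in dissolution can alter how early the peak occurs as well as how high it is. The design pairs every test batch with the reference in the same person, but the tmax table does not use that pairing. A reader who wants the shift in tmax for Batch B against Batch A must compare two marginal medians by eye, with no measure of uncertainty.

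The coarse sampling makes that comparison less reliable. tmax can only be the time of a sample, so medians move in jumps. Near-equal medians do not establish similar timing, and medians one step apart do not establish a shift. At stake is how well one secondary endpoint is described. The primary comparison is not affected.

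**Working it through.** The documents state no tmax value, variability or expected shift, so there is no planned figure to reproduce.

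**Inputs from the documents**

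- Maximum number of participants: 4 sequences × 7 = 28 (Protocol 6.3.1). The planned number is redacted.
- Sampling steps up to 8 h (Protocol 1.3): 0.25 h between 0.25 and 0.5 h; 0.5 h between 0.5 and 3 h; 1 h between 3 and 4 h; 2 h between 4 and 8 h.
- Sampling windows (Protocol 8.4.1, Table 1): ±2 min up to 1 h, ±5 min from 1.5 to 12 h.
- Interval level: 90%, as for the primary endpoints.

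**Assumptions**

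- Lognormal tmax with a reference value of 0.75 to 1.5 h.
- Between- and within-participant SDs of log tmax both 0.35.
- A true 30% delay is 0.30 × 0.75 = 0.225 h to 0.30 × 1.5 = 0.45 h, which is under one 0.5 h step.

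**Method.** Each simulated tmax is moved to the nearest sampling time. For actual times, it is then shifted at random within the allowed window. Two summaries are compared:

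1. Planned: median(test) − median(reference).
2. Paired: with dᵢ = test − reference in participant i, the Hodges-Lehmann estimate is the median of the averages (dᵢ + dⱼ)/2 for i ≤ j. With 28 participants there are 28 × 29/2 = 406 averages. The 90% limits are about the k-th smallest and k-th largest, where k ≈ 203 − 1.645 × √(28 × 29 × 57/24) = 203 − 1.645 × 43.9 ≈ 131.

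**Results, 30% delay (range over the reference tmax values)**

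| | Nominal times | Actual times |
|---|---|---|
| Batch medians identical | 14% to 40% | 0% |
| Batch medians within 0.1 h | – | 11% to 42% |
| Hodges-Lehmann estimate within 0.1 h of zero | – | 3% to 12% |
| Paired 90% CI above zero | 34% to 55% | 74% to 81% |

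The actual-times column matches the planned derivation of tmax. Exact ties disappear, but near-ties remain about as common. The CI does better there because nominal times produce many differences of exactly zero, which hold the lower limit at zero.

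**With no true delay**, on nominal times, the two medians still differ in about 8% to 50% of trials. On actual times the paired CI lies wholly above zero in 4% to 6%, close to the nominal 5%.

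**Where the problem stops.** A separate simulation used a mean tmax of 1.5 h, a between-participant SD of 0.4 h, within-participant SDs of 0.2 to 0.5 h and 20 to 28 participants, on nominal times. A 0.25 h delay left the medians identical in 36% to 41% of trials. A 0.5 h delay did so in only 1% to 7%.

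**The case against.** A reader might infer that tmax is the planned parameter most closely tied to dissolution, that the pairing is thrown away, and that a real delay would be reported as no difference. The documents do not support any of these.

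- No section ranks tmax that way. Protocol 2.1 names Cmax and AUC0-∞ as the primary parameters.
- The summary table is unpaired, but the by-participant listings and overlaid profiles keep the pairing. The minimum, maximum and tlag are also planned.
- Protocol 9.1 makes the analysis purely descriptive, and no conclusion of equal tmax is planned.
- Cmax also responds to absorption rate and is modelled within participant. In a one-compartment simulation (reference absorption rate 2/h, half-life 2 h), tmax shifts of 0.33 and 0.56 h came with mean Cmax ratios of about 0.90 and 0.84. A slow batch would not be invisible.

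These points stand and limit the weight of the concern. They do not supply an estimate of the timing shift: listings and plots give no interval, and a lower Cmax does not measure timing.

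The strongest statistical objection is that the remedy may do no better than the medians. On nominal times, with a 30% delay, the paired CI fails to exclude zero in 100 − 55 = 45% to 100 − 34 = 66% of trials, more often than the medians tie. But that sets an interval against a point estimate. Comparing point estimates on the actual times that the plan uses, near-zero results fall from 11% to 42% down to 3% to 12%. It remains true that the paired estimate is also limited by sample spacing: on nominal times, 78% to 89% of single-trial estimates fell on two or three values.

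**Conclusion.** The gap is real but modest. A crossover study of batches selected for differing dissolution plans no within-participant estimate or interval for tmax. The risk of misreading is mainly confined to delays shorter than about one sampling step. Under the assumed values, a 30% delay (0.225 to 0.45 h) leaves medians within 0.1 h in about 11% to 42% of trials; the paired estimate is that close to zero in about 3% to 12%, and its 90% CI lies above zero in about 74% to 81%. Delays of a full step or more usually move the median.

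All these percentages depend on assumed tmax values and SDs, and on 28 participants, the stated maximum. That no paired contrast is planned does not depend on them. The primary analysis is unaffected.

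**What to change.** In SAP 16.1.3, under secondary endpoints, add for B-A, C-A and D-A the Hodges-Lehmann median of within-participant tmax differences with a non-parametric 90% CI. Use actual times and label the result descriptive, consistent with Protocol 9.1. Keep the by-batch n, minimum, median and maximum.

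The cost is one extra descriptive table. It needs no new samples, no more participants and no change to the primary analysis. The table should carry a note that sampling intervals still limit the precision of the estimate, so that small shifts are not over-read.

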16.1.3 Statistical Analysis of PK Parameter Data

Analysis of Primary Endpoints

A linear mixed model with BATCH, PERIOD, and SEQUENCE as fixed effects and SUBJECT within SEQUENCE as a random effect will be applied to log-transformed primary endpoints C_{max} and $AUC_{0-\infty}$ based on the PK analysis set. Differences between batches (treatment A will be used as 'reference') on the log scale for each comparison will be estimated for the parameters together with their 90% CIs. Point estimates and CIs will be back transformed to the original scale by exponentiation for presentation. Ratio of geometric LSMEAN with 90% CI and geometric LSMEAN with 95 % CI will be presented.

Analysis of Secondary Endpoints

Summary statistics of PK parameters will be provided by study intervention.

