### 3 Objectives and Endpoints

Objectives	Endpoints
Primary	
To compare the single-dose PK of different manufacturing batches of evobrutinib TF2 formulation relative to a reference batch under fasted conditions in healthy participants	$AUC_{0-\infty}$ , $C_{max}$
Secondary	
To assess the safety and tolerability of evobrutinib administered as a single oral dose of different manufacturing batches of TF2 formulation under fasted conditions in healthy participants	Nature, occurrence, and severity of treatment-emergent adverse events (TEAEs) Absolute values and changes in safety laboratory tests Single 12-lead ECGs evaluated by Investigator (morphology and time intervals). Listing of the ECG description if classified as "abnormal". Vital signs assessed from time of first dose to end of study participation
To further characterize the PK of different manufacturing batches of evobrutinib TF2 formulation	Additional PK parameters: e.g. $AUC_{0-tlast}$ , $t_{max}$ , $t_{1/2}$ , $CL/F$ , $Vz/F$ , $F_{rel}$

ECG = Electrocardiogram, TEA = Treatment-emergent adverse event, TF2 = Tablet formulation 2.

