To assess the safety and tolerability of evobrutinib administered as a single oral dose of different manufacturing batches of TF2 formulation under fasted conditions in healthy participants	Nature, occurrence, and severity of treatment-emergent adverse events (TEAEs) Absolute values and changes in safety laboratory tests Single 12-lead ECGs evaluated by Investigator (morphology and time intervals). Listing of the ECG description if classified as "abnormal". Vital signs assessed from time of first dose to end of study participation
To further characterize the PK of different manufacturing batches of evobrutinib TF2 formulation	Additional PK parameters, e.g. $AUC_{0-\text{last}}$, t_{max} , $t_{1/2}$, CL/F, V_z/F , F_{rel}

6 Overview of Planned Analyses

The final, planned analyses identified in the CSP and in this IAP will be performed after the last participant has completed the last visit and after all data queries resolved as well as the database locked.

A data review meeting will be held prior to database lock for the final analysis. In addition, no database can be locked until this IAP has been approved.

7 Changes to the Planned Analyses in the Clinical Study Protocol

There are no changes to the planned analyses in the clinical study protocol.

8 Analysis Sets and Subgroups

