16.1.5.1 Estimation of Pharmacokinetic Parameters in Plasma

PK parameters will be calculated using the actual elapsed time since dosing. If the actual sampling time is missing, calculations may be performed using the scheduled time. Details (e.g., number of samples, participants affected) will be described in the CSR. If actual dosing time is missing, scheduled time might be used for NCA after performance of adequate plausibility checks and agreement with the sponsor. Decision and rational should be included in the CSR. Otherwise, there will be no further imputation of missing data.

The following plasma PK parameters will be calculated, when appropriate, for evobrutinib on Day 1 for each period:

Symbol	Definition
$AUC_{0-\infty}$	The AUC from time zero (= dosing time) up to infinity with extrapolation of the terminal phase.
$AUC_{0-t_{last}}$	The AUC from time zero (= dosing time) to the time of the last quantifiable concentration (t_{last}).
C_{max}	Maximum observed concentration.
t_{max}	The time to reach the C_{max} in a dosing interval.
$t_{1/2}$	The terminal half-life.
t_{lag}	The time prior to the first concentration at or above LOQ.
CL/F	The apparent total body clearance following extravascular administration.
V_z/F	The apparent volume of distribution during the terminal phase following extravascular administration.
F_{rel}	Relative Bioavailability [%] of each Batch in relation to the Reference Batch (treatment A) will be calculated: $F_{rel} = 100 \times (AUC_{0-\infty} \text{ [Batch]} \times \text{Dose}_{\text{[Reference Batch]}}) / (AUC_{0-\infty} \text{ [Reference Batch]} \times \text{Dose}_{\text{[Batch]}})$
λ_z	Terminal first order (elimination) rate constant.

Additional PK parameters may be calculated where appropriate.

Units for PK parameter outputs will be based on concentration and dose units used in the study, unless otherwise specified. If concentration data units change within the study, PK parameters will be reported using consistent units throughout study outputs. In such cases, the Sponsor will specify relevant units for reporting before the final PK evaluation.

The parameters C_{max} and t_{max} will be obtained directly from the concentration-time profiles. If C_{max} occurs at more than one timepoint, t_{max} will be assigned to the first occurrence of C_{max} .

The following PK parameters will be calculated for diagnostic purposes and listed, but will not be summarized:

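### Does the SAP need an upper-bound versus lower-bound (C versus B) contrast in addition to the comparisons with Batch A?

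*SAP*

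**What the plan says.** SAP section 16.1.3 fits a linear mixed model to log Cmax and log AUC0-∞, with batch, period and sequence as fixed effects and subject within sequence as a random effect. On the comparisons it says "Differences between batches (treatment A will be used as" the reference, which gives B/A, C/A and D/A. On output it adds: "Ratio of geometric LSMEAN with 90% CI and geometric LSMEAN with 95 % CI will be presented". Relative bioavailability in SAP section 16.1.5.1 has the same anchor: "Relative Bioavailability [%] of each Batch in relation to the Reference Batch (treatment A) will be calculated".

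Protocol section 9.4.3 describes the same model without naming a reference in that sentence: "Differences between batches on the log scale for each comparison will be estimated for the parameters together with their 90% CIs". SAP section 7 states: "There are no changes to the planned analyses in the clinical study protocol".

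The primary objective (protocol section 3, repeated in SAP section 5) is "To compare the single-dose PK of different manufacturing batches of evobrutinib TF2 formulation relative to a reference batch under fasted conditions in healthy participants". Protocol section 2.1 describes the batch choice as "1 each of lower and upper dissolution bounds (termed side batches), 1 batch as a reference", plus a hammer-milled fourth batch. Just before that description, it says that relative bioavailability is judged against the reference batch. Protocol section 9.1 calls the analysis purely descriptive, with no hypothesis tests.

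**The concern.** Protocol section 2.1 names the design: "This approach, referred to as mapping methodology, is described in the FDA guidance". Among the three conical-milled batches, what the design varies is the dissolution span from B to C, and no visible passage plans an estimate or interval for C/B. Protocol section 9.4.3 leaves the comparisons open while the SAP fixes them to A, so the SAP can look like an undeclared narrowing.

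Ratios multiply. If B lies somewhat below A and C somewhat above it, each may look acceptable against A while C and B are further apart. A reader could then conclude that the whole dissolution range is harmless for exposure when the two ends differ more than either planned ratio shows. Both planned ratios also share Batch A, which suggests that a C/B interval cannot be built from them.

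**Working it through.** **What the plan sets out to estimate.** The objective, the rationale in protocol section 2.1, the design rationale in protocol section 4.2 and the Frel definition all take the reference batch as comparator. Read with them, the comparisons in protocol section 9.4.3 are those against A. Naming A in the SAP makes the protocol explicit and is consistent with the SAP's statement that nothing changed.

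**Whether C/B can be recovered.** The plan prints no precision figure to reproduce; the planned sample size and the CV are not visible.

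Inputs:
- N = 28, from protocol section 6.3.1: at most 7 per sequence × 4 sequences.
- Sequences ABCD, BDAC, CADB, DCBA, from the same section.
- Within-participant CV of 20% and a yardstick of 0.80–1.25. Both are assumptions for illustration; the visible text gives neither.

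With complete data there are 28 × 4 = 112 observations. Residual df = 112 − 1 − 27 − 3 − 3 = 78. The design matrix with subject, period and batch effects gives

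var(B−A) = var(C−A) = var(C−B) = 2σ²/28 = 0.0714σ².

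σ = √ln(1 + 0.20²) = 0.198, and t(0.95; 78) = 1.665.

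90% CI factor = exp(1.665 × 0.198 × √(2/28)) = exp(0.0881) = 1.092.

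| Ratio | Estimate | 90% CI |
|---|---|---|
| B/A | 0.90 | 0.82–0.98 |
| C/A | 1.11 | 1.02–1.21 |
| C/B = 1.11/0.90 | 1.23 | 1.13–1.35 |

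The third row needs only the first two: divide the estimates and apply the same factor. Sharing Batch A is no obstacle, because in this balanced design the shared term leaves C−B with the same variance as the printed contrasts.

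**Incomplete data.** I removed random participants from a random period (2 to 4) onward, 2,000 draws each. SE(C−B) stayed within about 3% of the mean of SE(B−A) and SE(C−A) with two dropouts, and within about 5% with four. A 5% change in the log half-width moves the C/B interval above from 1.13–1.35 to 1.12–1.35 (wider) or 1.13–1.34 (narrower).

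**Whether the example hides anything.** Both planned intervals exclude 1, B/A from below and C/A from above. The planned table would itself show B under A and C over A. The C/B estimate, 1.23, lies inside 0.80–1.25; only its upper confidence limit passes 1.25. That is imprecision against a borrowed yardstick and contradicts nothing the trial plans to say.

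**The case for a change.** The strongest case puts both planned intervals at the edge of 0.80–1.25 with N = 28. At CV 20%, B/A = 0.874 and C/A = 1.145, so C/B = 1.31 (90% CI 1.20–1.43), and the estimate itself is outside. At CV 30%, B/A = 0.912 and C/A = 1.097, so C/B = 1.20 (1.06–1.37). There the planned intervals include 1 (0.912 × 1.14 = 1.04; 1.097 / 1.14 = 0.96) while the C/B interval does not. At CV 40%, C/B = 1.11 (0.93–1.32). At CV 50% the effect is marginal, and at N = 20 to 24 it disappears. So C/B can carry information that neither planned ratio shows alone. The per-batch geometric means with 95% CIs do not replace it, since those intervals include between-participant variance. A C/B ratio computed after the results are seen would count as unplanned under SAP section 4.

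This arithmetic stands, and so does the point that the row would cost almost nothing. The step to a defect does not follow. In each of these cases the reader reaches the same C/B interval from the printed ratios, exactly with complete data and closely with a few dropouts. The harm also needs an acceptance range and a planned conclusion about the whole range, and the visible text has neither. Nothing visible says that mapping requires upper against lower bound; that would rest on cited guidance outside the documents. Nor is C/B known to be the widest contrast: hammer-milled Batch D is not placed on the dissolution scale, and the order of the batches in vivo is unknown.

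**Conclusion.** The concern does not hold. The SAP estimates what the objective asks for, comparison with Batch A, and those estimates and their interpretation are sound without C/B. What is missing is one printed row. With 28 participants and complete data that row follows exactly from B/A and C/A; with four random dropouts its standard error is recovered within about 5%. Naming the C/B contrast would be a reasonable optional addition, but it corrects no planned result or conclusion.

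This rests on the maximum of 7 participants per sequence being enrolled and on dropout being limited and random. The equality of the three variances does not depend on the CV; the illustrated intervals assume 20% and the 0.80–1.25 yardstick. Parts of protocol sections 4.2 and 9 are redacted, so an acceptance range or a further comparison could be stated there; the judgement is on the visible text.
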